Goals	
The main objective is to validate the performance of the measurement of the heart rate (HR) measured by the COBOX medical device compared to a measurement carried out by applying the reference processes for taking measurements via a CE marked device. The concordance between the two measurement methods is sought here.
 
The secondary (ranked) objectives of the study are:
 
 - Evaluate the performance of the measurement of the respiratory rate (RR) measured by the COBOX medical device compared to a measurement carried out by a reference method of manual counting . - Establish and verify the clinical safety of COBOX and detect any adverse side effects under normal conditions of use of the device and assess whether these constitute an acceptable risk in relation to the expected benefits of the device concerned.
Research scheme	Clinical, prospective and observational investigation
Inclusion criteria	
- Adult patient (18 years and over)
 
And

	
-Patient consultant in the emergency department of a participating center
 
And
 
 - Patient having constant FC and FR taken by the reception organizing nurse (IOA) in the area dedicated to the reception of patients 
And.
 
 - Patient having given their consent to participate in the study.
Non-inclusion criteria	
 - Patient in a state of vital emergency with direct entry into SAUV or intensive care. - Patient who did not consent to participate in the study. - Patient unable to express consent. - Patient unable, for health reasons, to face the COBOX solution. - Patient unable to stand for 30 seconds facing the COBOX solution . - Patient with skin stigma over more than 50% of the face (burn, graft). - Patient having the face covered or not allowing access to the entire face (clothing).
Treatments/Strategies/ research procedures	
The patients included in the study will have their HR and HR constants taken simultaneously at the reception of the emergencies by a reference medical device and by COBOX.

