In current practice, measurements of respiratory rhythms and frequencies are taken visually by identifying the movements of the rib cage: The operator (nursing staff or arc or medical or paramedical tec) in current practice counts the complete respiratory movements (inspiration + exhale) for 30 seconds and multiply by 2 to extrapolate the result to 1 minute (Cycles per minute).

This medical decision-making can therefore vary according to these results, 2 to 3 cycles per minute varying around a "risk zone" (Above 20 cycles/minute or below 12/minute) can decide to whether or not to put on oxygen (these results are always interpreted with the oxygen saturation). Beyond the lack of robustness and reproducibility of this measurement in routine care, the purely human intervention makes its regular or continuous monitoring complex and time-consuming.

Finally, this data without a real monitoring standard is data that is almost unusable in epidemiological and/or clinical research.

Potential side effects

There are no direct or indirect adverse effects for the patient identified to date.

Residual risks associated with the experimental device, as identified in the risk analysis report

After implementation of risk reduction actions (in accordance with document REC-M2-016 Product risk analysis of the Technical File), all the residual risks assessed are deemed acceptable.

Risks associated with participating in the clinical investigation

No associated risk has been identified, the non-inclusion measures having been identified in this regard. The data collected for the evaluation will be observational and the information provided by COBOX will not be used in clinical decision-making.

Possible interactions with concomitant medical treatments

No interactions have been identified.

Measures that will be taken to control or mitigate the risks

The COBOX application poses no risk to the patient.

Justification of the risk/benefit ratio

As stated previously, the implementation of the risk management process led to the absence of unacceptable residual risks for the conduct of this study. Furthermore, the assessment of the benefit/risk is the subject of provisions documented within the PRO-M2-004 Risk Management procedure.

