It follows that the absence of unacceptable residual risk and the identification of expected clinical benefits, established on the basis of preclinical performance verification trials, are such as to establish a favorable benefit/risk ratio for the conduct of the study. .

5. Objectives and hypotheses of the clinical investigation

Research hypotheses and expected results

In order to meet safety and quality standards, new health technologies require rigorous clinical validation with measurement performance at least equivalent to that obtained through the application of reference measurement processes using marked devices. CE, as well as those obtained via the manual counting reference method.

In this context, we hypothesize that the COBOX device will take measurements of heart and respiratory rates consistent with those obtained through the application of reference processes for taking measurements via CE marked devices, as well as those obtained via the manual counting reference method.

We also make the assumption of an economic superiority by a release of time allowed by the automation of these catches, and the suppression of the protocols of decontamination allowed by the taking of measurement remotely.

The tool (COBOX) will reduce the cognitive load of caregivers in favor of a higher quality of care. It will also allow greater access to vital sign measurements thanks to its purely software nature and requiring only a smartphone or tablet (or a computer or any other device with a camera).

Primary objective

The main objective is to validate the performance of the measurement of the heart rate (HR) measured by the COBOX medical device compared to a measurement carried out by applying the reference processes for taking measurements via a CE marked device. The concordance between the two measurement methods is sought here.

Secondary objectives

The secondary (ranked) study objectives are:

- Evaluate the performance of the measurement of the respiratory rate (RR) measured by the COBOX device compared to a measurement carried out using the manual counting reference method. The concordance between the two measurement methods is sought here.
- Evaluate the additional parameters allowing to establish the clinical performance of COBOX for the measurement of HR and RR:
 - o Measurement repeatability.
 - o The accuracy of the measurement: concordance within a tolerated margin between the measurement taken by the COBOX device and current practices.

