COBOX is a tool for measuring cardiac and respiratory rhythm in routine clinical practice for patients outside intensive care and outside continuous monitoring. We expect a correlation coefficient of more than 0.7 between the COBOX measurements and those obtained using the reference method. Regarding the secondary endpoints, we expect average standard deviations

between COBOX and the reference methods of 5 bpm for the heart rate and 3 bpm for the respiratory rate.

Expected benefits

These data will validate the COBOX tool in terms of measurement performance compared to the results obtained through the application of reference processes for taking measurements using CE marked devices, as well as those obtained using the reference method of counting manual. Applications for taking physiological constants without contact have a wide field of application in the field of routine care and save medical time, increase quality by limiting manual copying errors and the risk of contamination.

6. Research design

Research scheme

This is an observational study, responding to Article 62.1 of the European medical device regulations, prospective, comparative.

Primary endpoint

The main judgment criterion will be the intra-class correlation coefficient between the measurement by COBOX and the measurement obtained thanks to the application of the reference processes for taking measurements via a measurement by a CE marked tool (for HR).

In order to ensure the repeatability of the device, three successive comparative measurements (each spaced 5 seconds apart) on the same patient will be carried out.

Secondary endpoints

The additional secondary judgment criteria will be:

- For RF (ranked criterion): comparison with a manual measurement following a reference method of manual counting according to good training practices for healthcare personnel trained in taking measurements (ide, as, internal external).
- The reliability of the reproducibility of the measurement
- The time in seconds dedicated to taking the parameters with and without the COBOX tool (time for installing and removing the tool if applicable, time for completing the medical file if applicable, effective time for taking the HR constants and FR).
- Assessment of treatment costs:
 - Pick-up times / delays
 - Total treatment costs (direct medical and non-medical costs)

Inclusion criteria

- Adult patient (18 years and over)
AND
- Patient consulting in the emergency department of a participating center
AND

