
QUANTIQ provides users with one tablet per site per physician. Delivery of a functional tablet in the event of a malfunction within 5 working days. Bug fix within 3 days in case of software malfunction with continuous information for professionals.

8. Research process

Research timeline

- Start of inclusions: Mid-July 2022
- Duration of the inclusion period: 2 months
- Duration of participation of each patient: The time of their passage in the IOA box (less than 30 minutes)
- Total research duration: 3 months

Summary of patient follow-up

- Oral information by the IOA. If necessary, an investigating physician can complete the information at the patient's request.
- Informed consent with electronic signature.
- Collection of the patient's age, gender and Fitzpatrick phototype.
- Collection of patient identification number.
- The nursing staff (or arc or tec) installs the oximeter on the patient's finger.
- The nursing staff (or arc or tec) starts COBOX and begins to count the breaths in parallel.
- After 15s, a first measurement is made by COBOX. The pulse oximeter reference result is acquired in parallel, associated with the patient ID number and stored with the COBOX result at the same time on an electronic database.
- After 20s (5s after the previous measurement), a second measurement is made by COBOX. The pulse oximeter reference result is acquired in parallel, associated with the patient ID number and stored with the COBOX result at the same time on an electronic database.
- After 25s (5s after the previous measurement), a third measurement is made by COBOX. The pulse oximeter reference result is acquired in parallel, associated with the patient ID number and stored with the COBOX result at the same time on an electronic database.
- After 30s, the nursing staff (or arc or tec) enters the number of breaths counted since the start. This result is converted into a respiratory rate (RR) then associated with the patient number and stored in the database.

The data is blocked on the database until the end of the study. At the end of the study, they will be sent to the coordinating centre.

In order not to disrupt the general operation of the emergency department and patient care, the usual patient circuit is not modified. The COBOX tool is used by the reception staff in a contemporary way to their usual collection of input parameters.

Collection of consent

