The information is compiled by the IOA and if necessary completed by a doctor. This information must make it possible to answer all the patient's questions concerning the objective, the nature of the constraints, the foreseeable risks and the expected benefits of the research. It also specifies the patient's rights in the context of a clinical investigation and verifies the eligibility criteria. A copy of the information note and the electronic consent form are then given to the patient by the investigating physician.

The consent form is electronic and must be signed before data can be collected for research. After electronic acceptance of the consent, a copy of the consent form is sent to the patient with his identification number allowing him at any time to ask the Sponsor to delete his data. For his part, the Sponsor only has access to the patient's identification number but his email address is not stored.

The data will include:

- Taking FC and FR by the reference method
- HR and FR taken by the COBOX tool at the same time as those of the reference tool.
- The patient's age, sex and Fitzpatrick phototype.

The different copies of the information notice and the consent form are then distributed as follows:

- A copy of the information note and the signed consent is given/sent by email to the patient.
- The original copy is kept by the investigating physician (even if the patient moves during the duration of the research) in a safe place inaccessible to third parties.
- When accepting the patient's participation on the electronic form. This is automatically sent to the Sponsor.

Search stopping rules

The temporary stoppage of the research can be pronounced by technical problems concerning the evaluated tool. The research stops definitively when the necessary number of subjects is reached and all the data allow the analysis.

Constraints related to research and possible compensation of subjects/patients

Patients can simultaneously participate in another research. No compensation is provided for in this study. The patient will not be registered in the national file of people who lend themselves to biomedical research.

9. Management of adverse events and new facts

In accordance with article 2 of regulation 745/2017, the following terms mean:

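### The secondary time endpoint contrasts measurement with and without COBOX, but COBOX always runs on top of the reference measurements and no per-tool times are planned, so the contrast cannot be delivered as written.

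*Combined protocol and SAP*

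**What the plan says.** - **Endpoint.** Section 6 (Secondary endpoints) lists "The time in seconds dedicated to taking the parameters with and without the COBOX tool". It names the parts: "time for installing and removing the tool if applicable, time for completing the medical file if applicable, effective time for taking the HR constants", with respiratory rate alongside. A separate item on the assessment of treatment costs covers pick-up times or delays and "Total treatment costs (direct medical and non-medical costs"; it names no comparison.
- **Purpose.** Section 5 (Research hypotheses and expected results): "We also make the assumption of an economic superiority by a release of time allowed by the automation of these catches". Section 5 (Justification of methodological choices) also announces a medico-economic study, without a design or data source.
- **Procedure.** The section 1 summary says that included patients "will have their HR and HR constants taken simultaneously at the reception of the emergencies by a reference medical device and by COBOX". Section 3 describes COBOX as additional to the reference methods. In section 8 (Summary of patient follow-up), staff place the oximeter, after which the staff member "starts COBOX and begins to count the breaths in parallel". COBOX and the oximeter are read at 15, 20 and 25 s, and the breath count is entered at 30 s. The usual patient circuit is left unchanged. Section 7 adds that the study oximeter is worn while the centre's own CE-marked device is in use.
- **Data.** The list in section 8 (Collection of consent) covers the reference readings, "HR and FR taken by the COBOX tool at the same time as those of the reference tool", and age, sex and phototype.
- **Use of results.** Section 4: "the information provided by COBOX will not be used in clinical decision-making".
- **Analysis.** Section 10 gives no method for time or cost.

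**The concern.** An endpoint worded as with versus without needs either observations made without COBOX, or separate times for each tool in the same patient. The procedure supplies neither. If staff follow section 8 exactly, the database will hold readings taken at preset seconds and nothing from which a time difference could be computed.

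The risk lies in the report. A time-saving or cost figure could appear as a finding of a prospective multicentre investigation when it actually came from assumption, or from the protocol's own clock. Section 5 already states the direction expected.

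**Working it through.** The plan gives no effect size, standard deviation or sample size for time or cost. Its only sample size is for the primary intraclass correlation, checked first for completeness.

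**1. The plan's own figure.** Inputs from section 10: ρ0 = 0.6, ρ1 = 0.7, k = 3, two-sided α = 0.05, power 90%, 30% unusable data. With θ = ρ/(1 − ρ), θ0 = 1.5 and θ1 = 2.333. C0 = (1 + 3 × 1.5)/(1 + 3 × 2.333) = 5.5/8 = 0.6875. The Walter–Eliasziw–Donner formula is n = 1 + 2(z for α/2 + z for power)² k / [(ln C0)² (k − 1)], which gives 225.5, rounded up to 226. Then 226/0.7 = 322.9, rounded up to 323. The figure reproduces, but it says nothing about time or cost.

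**2. Observations without COBOX.** All 323 planned patients have both methods at once. No arm, period or sequence omits COBOX. Patients who decline do not get COBOX, but section 8 requires signed consent before research data are collected, so they contribute no times. Planned observations without COBOX: 0 of 323.

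**3. Session time.** Let R be the time for the reference sequence (oximeter on, 30 s count, oximeter off, record entry). COBOX is added to that sequence and replaces none of it, so joint session time J = R + a, where a ≥ 0 is any extra handling for COBOX. Hence J − R ≥ 0. On this reading a saving cannot appear, and R is never observed alone.

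**4. Effective measuring time.** The times are prescribed: first COBOX reading at 15 s, last at 25 s, manual count ending at 30 s. The gaps, 30 − 25 = 5 s and 30 − 15 = 15 s, are constants of the protocol and would be the same in every patient who follows it. They are not outcomes.

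**5. What could be compared within a patient.**

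| Component named in section 6 | Separable by tool? | Recorded under sections 8 and 10? |
|---|---|---|
| Installing and removing the tool | Yes: oximeter handling against COBOX set-up | No time planned |
| Completing the medical file | Yes, if each entry is timed | No time planned |
| Effective measuring time | Fixed by the clock | Constant |

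**6. Delays and costs.** Each patient has one delay and one total cost, both arising under joint use. COBOX readings do not inform care and the circuit is unchanged, so neither quantity carries a contrast attributable to COBOX.

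**7. Device costs.** The section 7 table covers the study oximeter: €242.50 over 2 years is €121.25 a year, plus €12.1 is €133.35, matching the stated €133.4. It has no row for COBOX or the tablet. A desk comparison is possible once that row is supplied, and it needs no patient data.

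**The case against.** The strongest defence is that section 6 defines the time endpoint by components, some marked as applying only where relevant. That wording suits timing each tool separately in the same patient and needs no COBOX-free group. The procedure in section 8 is headed as a summary. Its data list sits under consent and is plainly incomplete, since it also omits adverse events and the caregiver questionnaire. On this view, times might be collected without being listed there.

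Part of this stands. Component timing is feasible, and a reader who infers that no time comparison could ever be made in this design goes too far. But no section of the plan says who records the times, how, or how they are analysed, and the measuring-time component would remain a constant.

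Three other stronger readings are not supported:

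- **That 5 s or 15 s is the most COBOX could save.** Those gaps leave out oximeter handling and file completion, both named in section 6.
- **That the cost difference is zero by design, or that cost too is framed as with versus without.** The wording of contrast belongs to time alone, and section 7 holds device-cost inputs that do not depend on COBOX changing care. The cost wording may itself be a translation problem.
- **That one person runs both methods.** Section 8 names a staff role. The argument does not need a single operator.

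The defence is also right that economic superiority is an assumption. It is absent from H0 and H1, from the listed objectives and from the sample-size basis.

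**Conclusion.** The point holds as a conflict between endpoint and procedure, limited to secondary endpoints. With 0 of 323 planned patients measured without COBOX, no planned time variable and no analysis, section 8 followed exactly does not yield the section 6 time endpoint. Joint-session time can only be equal or longer with COBOX, and effective measuring time is fixed in advance. Patient-level delays and total treatment costs observed here cannot be attributed to COBOX.

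This rests on three assumptions: that the reference sequence is performed in full in every patient, as section 8 states; that no timing procedure exists outside these documents; and that delays and treatment costs carry their ordinary meaning of patient-level quantities. If the sponsor meant device costs only, the cost part becomes a matter of wording. No corrected number applies. The primary heart rate and ranked respiratory rate analyses are unaffected, so this is a worthwhile, inexpensive correction and does not threaten the trial's main result.

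**What to change.** 1. **Either capture component times.** Have the tablet application time-stamp, per patient: oximeter on and off, manual count start and stop, COBOX set-up and start, the COBOX reading that counts as final, and record entry for each tool. The consent step belongs to the research and should be excluded.
2. **Redefine the endpoint** in section 6 as the paired within-patient difference D = (sum of reference-only components) − (sum of COBOX-only components). State that measuring time is fixed by protocol, and say which COBOX reading closes the interval. In section 10, report D descriptively with a 95% confidence interval, labelled as a proxy for workflow.
3. **Or delete** the time endpoint that contrasts use with non-use.
4. **In either case**, do not present patient-level delays or total treatment costs as COBOX effects from this study. Clarify what the cost item means. Assign the economic-superiority assumption to the announced medico-economic study; any device-cost comparison should include a row for COBOX and the tablet.

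The cost is a few extra taps per patient and a few lines in sections 6, 8 and 10, with no extra patients or staff. The limitation is that component times recorded while both methods run together only approximate real working practice.

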Source: AT Ayance, HS Ramírez, JMR Pérez and CGT Palacios, "Low-cost microcontrolled based wireless heart rate and oxygen saturation monitor," 2018 International Conference on Electronics, Communications and Computers (CONIELECOMP), 2018, pp. 176-180, doi: 10.1109/CONIELECOMP.2018.8327195.

The rPPG on the other hand works on the same basic principle as the PPG in reflection except that the ambient light plays the role of the LED and the camera the role of the photodetector (see figure 2).

[figure not shown]

Figure 2. Light path in skin for a) contact PPG b) remote PPG

Source: Verkruyse, Wim PhD*; Bartula, Marek MSc†; Bresch, Erik PhD‡; Rocque, Mukul MSc†; Mestah, Mohammed BSc†; Kirenko, Ihor PhD† Calibration of Contactless Pulse Oximetry, Anesthesia & Analgesia: January 2017 - Volume 124 - Issue 1 - p 136-145 doi: 10.1213/ANE.0000000000001381

In its current version, the technologies embedded in this SaaS platform (COBOX) allow remote tracking, calculation and processing of several biological markers (cardio-respiratory rate). The idea is therefore to transform any camera into a medical device. From this camera. It is a SaaS platform type product that can be integrated and integrated into any other existing or future device. The data can be sent to the patient and the practitioner or managed in real time by trained and qualified nursing staff.

Finally, for its operation, the SaaS API requires a high-speed internet connection and an image capture device by optical camera.

The objectives of this solution are multiple:

- Standardization & reproducibility of the measurement :

Taking the constant "manually" by observation is today the reference method for measuring the respiratory rate. According to good training practices for medical or paramedical nursing staff, this method consists of counting the respiratory movements (inspiration and expiration) of the rib cage for 30 seconds extrapolated to 1 minute (by multiplying the value by two). This technology makes it possible to standardize the measurement of the respiratory rate by a reproducible and repeatable method with considerably reduced operator bias.

- Save time by automating vital signs measurements

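### Section 8 does not keep COBOX respiratory-rate output from the operator before the manual count is saved, so the RR reference is open to being drawn toward the device

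*Combined protocol and SAP*

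**What the plan says.** The sequence is in section 8, Summary of patient follow-up:

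- Start: the nurse, arc or tec "starts COBOX and begins to count the breaths in parallel".
- 15 s: "After 15s, a first measurement is made by COBOX". A second reading follows at 20 s.
- 25 s: "After 25s (5s after the previous measurement), a third measurement is made by COBOX".
- 30 s: "After 30s, the nursing staff (or arc or tec) enters the number of breaths counted since the start". The count is then converted to a rate and stored.

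Section 3 (Model/type name) puts the DemoCOBOX application on a study tablet. Section 12 (Guidelines for data collection) requires all protocol information to be recorded in the tablet. Section 8 (Collection of consent) confirms that COBOX takes RR as well as heart rate (HR) at the same time as the reference.

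The protocol has a low opinion of manual counting. Section 3 says COBOX standardises RR "with considerably reduced operator bias", which implies that the manual method carries such bias. Section 4 (Clinical benefits) says of manual RR measurement: "Beyond the lack of robustness and reproducibility of this measurement in routine care". The summary in section 1 describes only the HR reference process as independent of the operator.

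RR agreement is the ranked criterion under Secondary endpoints in section 6. The only text resembling a safeguard is the section 8 statement that data stay locked in the database until the study ends.

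**The concern.** In a method-comparison study the reference should be fixed without knowledge of the test result. Here the reference is a human count, made while attending to the device under test and recorded after that device has taken its three readings. If a COBOX RR is on the screen by then, an operator unsure whether one more movement counted as a breath has a number to settle the doubt.

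Such an error favours the device. It shrinks the differences in the Bland-Altman analysis and the mean square error, and it raises the ICC, without COBOX being any more accurate. No analysis in section 10 could undo it, because the uninfluenced count would not exist.

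The unit of error is not small on the protocol's own scale. One breath in 30 s is 2 cycles/min. Section 4 treats 2 to 3 cycles/min as enough to matter near its risk thresholds, and section 5 expects a spread of 3 per minute between COBOX and the RR reference.

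HR does not share the problem, because the oximeter value is acquired and stored electronically alongside the COBOX result.

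**Working it through.** **What is and is not affected.** The study size in section 10 reproduces from its own inputs: minimum ICC 0.6, expected ICC 0.7, k = 3, two-sided alpha 0.05, power 90%.

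- θ0 = 0.6/0.4 = 1.5; θ1 = 0.7/0.3 = 2.333; C = (1 + 3 × 1.5)/(1 + 3 × 2.333) = 5.5/8 = 0.6875
- n = 1 + 2(1.960 + 1.282)² × 3 / [(ln 0.6875)² × 2] = 225.5, rounded up to 226; 226/0.70 = 323

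None of these inputs depends on the breath count, so the sample size and the primary HR ICC stand.

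**Assumptions for the RR illustration (none is in the documents).**

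- One COBOX value and one count per patient, no mean bias.
- Between-patient RR SD s of 3, 4 or 5 cycles/min. The count comes in steps of 2 cycles/min, which adds 2²/12 = 0.333 to its variance, so V = s² + 0.333.
- True COBOX-minus-count difference D, normal with SD d of 3, 4 or 5.
- When |D| is 2 or more, the operator moves the count one breath (2 cycles/min) toward COBOX with probability p.
- ICC of the one-way form. The protocol does not state a form.

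**Formulas.** Let q = P(|D| ≥ 2) = 2[1 − Φ(2/d)], and let m = 2d·φ(2/d), the mean of |D| counted only where |D| ≥ 2.

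- Variance of the recorded difference = d² − 4pm + 4pq
- ICC = 2(V + 2pm) / (2V + 4pq + d²)

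**Worked case, s = 4 and d = 4.** V = 16.333, q = 0.617, m = 2.817.

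- p = 0: ICC = 32.667/48.667 = 0.67; SD 4.0
- p = 0.25: ICC = 2(16.333 + 1.408)/(32.667 + 0.617 + 16) = 35.48/49.28 = 0.72; SD = √(16 − 2.817 + 0.617) = 3.7
- p = 0.50: ICC = 2(16.333 + 2.817)/(32.667 + 1.234 + 16) = 38.30/49.90 = 0.77; SD = √(16 − 5.633 + 1.234) = 3.4

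**All nine combinations.** For d = 3, q = 0.505 and m = 1.917. For d = 5, q = 0.689 and m = 3.683. A simulation of one million pairs per combination agrees with these values to within about 0.001.

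| RR SD s | Difference SD d | ICC, no shift | ICC, p = 25% | ICC, p = 50% |
|---|---|---|---|---|
| 3 | 3 | 0.67 | 0.73 | 0.78 |
| 3 | 4 | 0.54 | 0.61 | 0.68 |
| 3 | 5 | 0.43 | 0.50 | 0.58 |
| 4 | 3 | 0.78 | 0.82 | 0.86 |
| 4 | 4 | 0.67 | 0.72 | 0.77 |
| 4 | 5 | 0.57 | 0.62 | 0.68 |
| 5 | 3 | 0.85 | 0.87 | 0.90 |
| 5 | 4 | 0.76 | 0.79 | 0.83 |
| 5 | 5 | 0.67 | 0.71 | 0.75 |

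The rise runs from about 0.02 (s = 5, d = 3, p = 25%) to 0.15 (s = 3, d = 5, p = 50%).

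- **Against 0.7:** three combinations start above it, three cross it at p = 25%, and three stay below it even at p = 50%.
- **Against 0.6:** two cross it (0.54 to 0.61 and 0.57 to 0.62), six start above it, and one stays below.

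**The case against.** The strongest reply is that the decisive fact is missing. Bias needs an operator who sees a COBOX RR before saving the count, and no section says that a value is displayed. Section 8 speaks only of storing results. Section 4 says COBOX information plays no part in clinical decisions, so showing it at the bedside has no stated clinical purpose.

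Nor is it certain that an RR exists before 30 s. The readings at 15, 20 and 25 s are paired with the oximeter, which is the HR reference, and the repeated-measures analysis in section 10 names heart rate only. Section 8 also names a staff role; a single operator is the natural reading, but two people are not excluded.

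All of this stands as a limit. A reader might infer that the study is run with the operator watching the COBOX RR, so that the reference is contaminated. The documents do not support that; they leave the matter open. The reply does not close the gap, however. The database lock governs stored data and not what the screen shows, and the written procedure permits an RR to be seen first.

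The size also rests on assumption. A reader might take the s = 4, d = 4 case as showing that anchoring would carry RR agreement past 0.7. That pair happens to start just below 0.7, and with a shift in only 5% or 10% of discrepant counts it reaches only 0.68 or 0.69. Nothing in the documents supports any particular shift frequency. The benchmarks need care too: 0.7 is an expectation, and 0.6 is the minimum set in the study size calculation.

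**Conclusion.** The point holds as an unprotected step in the procedure and not as a demonstrated bias. Staff in the role that starts COBOX also count the breaths and enter the count after the three COBOX readings, on the tablet that runs COBOX, and no masking is described. If a COBOX RR is visible before the count is saved, agreement on the ranked secondary RR criterion can be inflated. If it is hidden, the effect is zero.

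Under the stated assumptions the ICC gain is about 0.02 to 0.15. These figures show direction and scale only, and no general claim about crossing 0.7 or 0.6 follows from them. The primary HR ICC and the sample size of 323 are untouched.

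**What to change.** In section 8, Summary of patient follow-up, require that DemoCOBOX show only a progress indicator during the 30 s. It should withhold all COBOX values until the manual count has been entered, time-stamped and locked against later edits.

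The cost is a short addition to the protocol and what should be a small change to the application, although the documents do not describe its screen. The operator sees the COBOX value a few seconds later. No extra staff or patients are needed. If the application already hides its output, only the protocol text is needed.
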